3.2.1 IgPro20

Subjects will receive IgPro20 infusions at a total weekly dose of 0.5g/kg split between 2 infusion sessions (eg, Day 1 and Day 3 or Day 4 for each week) every week. The total dose / volume of IP will be calculated based on body weight (see [Section 3.2](#)).

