3.2.2 IgPro10

Subjects will receive IgPro10 at a total dose of 2 g/kg split over 2, 3, 4, or 5 consecutive days, depending on total dose and individual tolerability, every 4 weeks. The total dose / volume of all IP will be calculated based on body weight. Changes of > 10% of body weight and the corresponding adjustment will follow the same way as IgPro20 in [Section 3.2](#).

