LLN	Lower limit of normal
CCI	CCI
MedDRA	Medical Dictionary for Regulatory Activities
CCI	CCI
PFT	Pulmonary function test
CCI	CCI
PID	Primary immunodeficiency
PK	Pharmacokinetics
SAE	Serious adverse event
SAF	Safety analysis set
SAP	Statistical analysis plan
SC	Subcutaneous
SD	Standard deviation
CCI	CCI
SMQ	Standardized MedDRA queries
SOC	System Organ Class
SSc	Systemic sclerosis
CCI	CCI
TEAE	Treatment-emergent adverse event
TEE	Thromboembolic event
CCI	CCI
ULN	Upper limit of normal
CCI	CCI

Glossary of Terms

Term	Definition
Baseline Value	The most recent assessment before the first infusion in Treatment Period 1.
End of Study (EOS)	The follow-up telephone call occurs 4 weeks after completing study treatment or early termination follow-up visit, whichever occurs later.
End of Treatment (EOT)	End of treatment is either end of Week 32 for completed subjects or at early termination visit.
Infusion	
IgPro10 An infusion comprises all IP exposure on one day of infusion. In the IgPro10 Treatment Periods, there are 2 to 5 consecutive days of infusions and so 2 to 5 Infusions planned per 4-week period.
 
IgPro20 An infusion comprises all IP exposure on one day (one session). In the IgPro20 Treatment Periods, there are 2 sessions and so 2 infusions planned per week.

Infusion Cycle (IgPro10 only)	One Infusion Cycle consists of 2, 3, 4 or 5 consecutive days of infusions with a planned total dose of 2 g/kg IgPro10 every 4 weeks. There are 4 planned Infusion Cycles of IgPro10 per IgPro10 Treatment Period in each Treatment Sequence.
Weekly Infusions (IgPro20 only)	A Weekly Infusion consists of 2 sessions (2 Infusions) with a planned total dose of 0.5 g/kg IgPro20 per week. There are 14 Weekly Infusions of IgPro20 per IgPro20 Treatment Period per each Treatment Sequence.
Infusion Session (IgPro20 only)	One Infusion Session consists of 1 infusion day. There are 2 Infusion Sessions within each weekly infusion with a planned total dose of 0.5 g/kg IgPro20 per week.
Protocol Deviation	
All instances when either subjects who have been entered in the study and / or the study sites deviate from the IEC / IRB-approved study protocol.
 
A key protocol deviation is any protocol deviation that could have a significant effect on the subject's safety, rights, or welfare and / or on the integrity of the study data.

Reference Visit	Reference visit for Treatment Period 1 is Week 1. Reference visit for Treatment Period 2 is Week 17.

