4.5 Determination of the Sample Size

The sample size for this study is not determined as based on hypothesis testing considerations. The sample size is mainly based on feasibility, not driven by power calculations for statistical hypothesis testing. However, based on the 9 IgPro20 studies completed by CSLB (8 studies on PID and 1 study in CIDP), the rate of ISRs per IgPro20 infusion is expected to be approximately 0.1, with 0.5 likely to be the maximum. With the target sample size of 20 subjects (10 subjects per Treatment Sequence) and each subject receiving 28 IgPro20 SC infusions, there are a total of 560 planned IgPro20 infusions overall

for the entire study. If the rate of ISRs per infusion is 0.1, the study will have 80% chance to have a 95% CI with half width ≤ 0.0261 using Wilson score method; if the rate is 0.5, the half width of the 95% CI will be ≤ 0.0414 .

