 - Causally related TEAEs by SOC and PT
 - Causally related TEAEs by SOC, PT, and maximum severity (without number of events)
 - Temporally associated TEAEs by SOC, PT and maximum severity (without number of events)
 - Temporally associated TEAEs and/or causally related TEAEs by SOC, PT and maximum severity (without number of events)
 - Serious TEAEs by SOC and PT
 - Serious, causally related TEAEs by SOC and PT
 - TEAEs leading to permanent discontinuation of IP by SOC and PT
 - Treatment-emergent AESIs by Category, SOC and PT
 - Treatment-emergent AESIs by Category and PT
 - Treatment-emergent AESIs by Category, PT and maximum grade (without number of events)
 - Treatment-emergent AESIs Grade 3 and above by Category and PT
 - Serious treatment-emergent AESIs by Category and PT

-
- Related treatment-emergent AESIs by Category and PT
 - All AE summaries presented by SOC and preferred term will include a virtual SOC “Infusion Site Reactions”, i.e., all AEs reported within the MedDRA High level terms “Administration site reactions NEC”, “Infusion site reactions” or “Injection site reactions”. AEs will be presented in the virtual SOC and the regular SOC.
 - All AE summaries presented by SOC and preferred term will include a virtual SOC “Thromboembolic Events” comprising all AEs reported within the MedDRA SMQs in [Section 11.3](#). AEs will be presented in the virtual SOC and the regular SOC.

Additional summary statistics for ISR will be presented for IgPro20 Treatment Periods only (see [Table 2](#)):

- Number and percent of subjects with ISR, incl. 95% Wilson score CI
- Number and percent of subjects with ISR per week, incl. 95% Wilson score CI
An ISR will be counted for the week of the most recent infusion before the onset of the ISR.
- ISR rate per Infusion
- ISR rate per Infusion per week
- Duration of ISR
- Time to onset of ISR since start of corresponding Treatment Period
- Time to onset of ISR since start of last infusion prior to onset of AE

$$\text{ISR rate per infusion} = \frac{\text{total number of ISRs across all subjects while on IgPro20}}{\text{total number of IgPro20 Infusions across all subjects}}$$

Temporally associated TEAEs are defined as AEs with an onset between the start of the infusion and up to 72 h after the end of infusion. In case time of onset of AE is missing, the AE is considered temporally related, if the onset of the AE is between the day of the start of infusion and the day of the end of infusion + 3 days (inclusive).

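### The single 72-hour rule for temporally associated TEAEs covers about 2.5 to 5 times as much of an IgPro20 period as of an IgPro10 period, so the by-product columns are not comparable

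*SAP*

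**What the plan says.** SAP 11.2 calls a TEAE temporally associated if it belongs to "AEs with an onset between the start of the infusion and up to 72 h after the end of infusion". If the onset time is missing, an onset date from the day the infusion starts to the third day after the day it ends counts instead. The rule is the same for both products.

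The SAP glossary sets the unit for IgPro10: "An infusion comprises all IP exposure on one day of infusion". The IgPro20 entry is equivalent, with one session per infusion. Every infusion day therefore opens its own window.

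The schedules differ sharply:
- **IgPro20.** Protocol 3.2.1 splits the weekly dose between "2 infusion sessions (eg, Day 1 and Day 3 or Day 4 for each week". The SAP glossary adds: "There are 14 Weekly Infusions of IgPro20 per IgPro20 Treatment Period per each Treatment Sequence".
- **IgPro10.** Protocol 3.2.2 has each 4-weekly dose "split over 2, 3, 4, or 5 consecutive days". The SAP glossary plans 4 such cycles per period.

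Temporally associated TEAEs appear in the SAP 11.2 overview table (subjects, percentages and event counts) and in two tables by SOC, PT and maximum severity. One covers temporally associated TEAEs alone and the other "Temporally associated TEAEs and/or causally related TEAEs by SOC, PT and maximum severity"; both omit event counts. Summaries are by product, by product and period, and in total. No adjustment for time inside the window is planned.

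**The concern.** A fixed window after each infusion captures background events in proportion to how often the product is infused. A headache unrelated to either product is more likely to fall within 72 hours of a twice-weekly infusion than of a 4-weekly cycle. The product columns would then differ because of the schedule alone.

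The direction matters here. Protocol 1.1 describes subcutaneous immunoglobulin as having fewer systemic reactions during or soon after infusion than the intravenous form, and Protocol 1.4.2.1 gives fewer systemic reactions as a possible benefit of IgPro20. A reader looking for that pattern would naturally turn to these tables, where the window rule works against it.

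There is also a problem within IgPro20: a flag that covers most of each dosing week says little about which events are linked to an infusion.

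**Working it through.** **Inputs.** The documents give no coverage figure. The infusion count behind it reproduces: 14 weeks x 2 sessions = 28 per subject, and 28 x 20 subjects = 560, as in SAP 4.5. A nominal period is 16 weeks = 112 days = 2,688 h. Infusion durations are not given; I assume 2 h for IgPro20, and for IgPro10 5 h (2-day cycle) or 3 h (5-day cycle).

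**Clock rule (onset time known).** Hours in the union of windows = (start of last infusion - start of first) + duration + 72, because consecutive windows overlap within a dosing week or cycle.

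- IgPro20, Day 1/3: 48 + 2 + 72 = 122 h a week; x 14 = 1,708 h; / 2,688 = 63.5%.
- IgPro20, Day 1/4: 72 + 2 + 72 = 146 h a week; x 14 = 2,044 h; / 2,688 = 76.0%.
- IgPro10, 2-day cycle: 24 + 5 + 72 = 101 h; x 4 = 404 h; / 2,688 = 15.0%.
- IgPro10, 5-day cycle: 96 + 3 + 72 = 171 h; x 4 = 684 h; / 2,688 = 25.4%.

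**Calendar rule (onset time missing).** Each infusion day covers 4 calendar days.

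- IgPro20: 6 or 7 days a week; 84/112 = 75.0% or 98/112 = 87.5%.
- IgPro10: 5 or 8 days a cycle; 20/112 = 17.9% or 32/112 = 28.6%.

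**Ratios, each within one rule.** Clock: 1,708/684 = 2.5 to 2,044/404 = 5.1. Calendar: 84/32 = 2.6 to 98/20 = 4.9.

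**Sensitivity.**
- Durations of 0.5-3 h (IgPro20) and 1-8 h (IgPro10) move clock coverage only to 62.8-64.1% or 75.3-76.6%, and to 14.4-15.5% or 25.1-26.2%.
- SAP Table 2 runs Period 2 to EOS, about 112 + 28 = 140 days. Coverage falls to 51-61% (clock) or 60-70% (calendar) on IgPro20, and to 12-20% or 14-23% on IgPro10. The ratio is unchanged because in-window time is unchanged.
- The protocol synopsis describes IgPro20 as given for 16 weeks, while the SAP glossary gives 14 weekly infusions. These passages need reconciling. With 16 dosing weeks, coverage would be 122/168 = 72.6% to 100%.

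**From events to subjects.** With an assumed constant background of m AEs per subject per 16 weeks, the chance of at least one flagged AE is 1 - exp(-m x coverage). Under the clock rule, for the pairings with the smallest and largest ratio:

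| m | Day 1/3 v 5-day cycle | Ratio | Day 1/4 v 2-day cycle | Ratio |
|---|---|---|---|---|
| 0.1 | 6.2% v 2.5% | 2.45 | 7.3% v 1.5% | 4.91 |
| 1 | 47.0% v 22.5% | 2.09 | 53.3% v 14.0% | 3.82 |
| 2 | 71.9% v 39.9% | 1.80 | 78.1% v 26.0% | 3.01 |
| 3 | 85.1% v 53.4% | 1.59 | 89.8% v 36.3% | 2.47 |
| 5 | 95.8% v 72.0% | 1.33 | 97.8% v 52.8% | 1.85 |

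The full ratio carries over to subjects only when the event is rare.

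**The case against.** The strongest reply has four parts.

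**The tables count subjects.** The two dedicated tables omit event counts, so it would be wrong to infer that every temporally associated table differs 2.5- to 5-fold. That ratio belongs to expected background event counts, which only the overview table shows, and to rare preferred terms. This stands.

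**The flag is not the same as any TEAE.** With recorded times, 24-36% of a 16-week IgPro20 period lies outside the windows. Full coverage of a dosing week needs both a Day 1/4 schedule and a missing onset time. A reader might infer that the combined temporal-or-causal table collapses into a table of all TEAEs; nothing in the documents lets that be calculated. This stands too.

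**Real infusion reactions are captured either way.** If intravenous reactions cluster during or soon after infusion, they fall inside the window however little of the period it covers. The artefact touches only the background component, so the net distortion is unknown. One cannot conclude that IgPro20 will look several-fold worse.

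**The tables are supportive.** Temporally associated TEAEs are not named in the primary or secondary endpoints (Protocol 2.1.2 and 2.2.2, SAP 4.2), and SAP 7.3 plans no hypothesis test. Calling them the core of the primary safety question would go too far. But descriptive percentages in adjacent product columns still invite comparison.

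Other planned outputs help only in part. All TEAEs and causally related TEAEs are tabulated, so a reader can see what share is flagged. The ISR rate per infusion and the ISR time-to-onset summaries are for IgPro20 periods only and do not correct these tables.

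**Conclusion.** The concern holds for comparability and for the flag's usefulness on IgPro20. The rule covers about 64-76% of a 16-week IgPro20 period against 15-25% for IgPro10 under the clock rule, and 75-88% against 18-29% under the missing-time rule. In a Period 2 that runs to EOS the figures are about 51-70% against 12-23% across both rules, with the same ratios within each rule.

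Expected flagged background event counts are therefore about 2.5 to 5 times higher on IgPro20 with no drug effect. Subject percentages differ about 1.8- to 3-fold at 2 assumed background AEs per subject per period, and 1.3- to 1.9-fold at 5.

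This rests on complete dosing as planned, a constant background rate that is equal for both products, and the assumed infusion durations, which hardly matter. The documents do not support a stronger reading in which IgPro20's observed safety profile is misstated by a known factor. The matter should be corrected, but it does not touch a primary endpoint.

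**What to change.** Keep the 72-hour flag and the planned tables. In SAP 11.2, add for each product:

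- the event rate per 100 in-window days beside the rate per 100 out-of-window days, counting days over the SAP Table 2 period;
- one window rule, the calendar-day rule, for all AEs in these rates. Otherwise events with and without times would be set against a person-time that fits only one group;
- in-window person-days under each column;
- a footnote that raw percentages of temporally associated TEAEs are not comparable between products, because window coverage differs by schedule.

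The cost is SAP wording and a little programming. Infusion start and stop times are already recorded (Protocol 5.1.3), and SAP 8.2.3 already derives time from the last infusion to AE onset.

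Two limits remain. In-window days carry different infusion densities: under the calendar rule, 28 infusions in 84-98 days on IgPro20 (0.29-0.33 a day) against 8 in 20 to 20 in 32 on IgPro10 (0.40-0.63 a day). The main reading is therefore the in-window against out-of-window contrast within each product. Also, a strict Day 1/4 subject has out-of-window days only after the last dosing week (112 - 98 = 14 in Period 1), so the IgPro20 out-of-window rate may rest on few, late days. Showing the person-days makes this visible.

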11.3 Adverse Events of Special Interest (AESIs)

In this study, hemolysis, TEEs, and acute renal injury will be treated as AESIs. The classification of AEs into AESI categories will be done using standardized MedDRA queries (SMQ).

In addition to the comprehensive search by SMQs, the site enters their assessment in the eCRF on whether the AE is of special interest. These entries are listed but not summarized.

All **hemolysis** events under the SMQ “hemolytic disorders, broad” will be considered AESIs.

The following 3 narrow SMQs will be utilized for **TEE** evaluation:

- Embolic and thrombotic events, arterial
- Embolic and thrombotic events, venous
- Embolic and thrombotic events, vessel type unspecified and mixed arterial and venous

All **acute renal injury** events under SMQ “acute renal failure, narrow” will be considered AESIs.

Descriptive tables for AESI will be generated similarly to TEAEs as described in [11.2](#).

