8.1.1.2 Hemolysis Safety Assessment

Clinical hemolysis will be assessed at time points as detailed in the [Schedule of Assessments](#). The time windows for each assessment are detailed in [Table 2](#).

Criterion A

- Drop in hemoglobin of > 1 g/dL within a 28-day interval since the time of last administration of IgPro10 without clinical evidence of blood loss from gastrointestinal bleeding, menorrhagia, hemoptysis, major hematoma, or injury and not explained by repeated phlebotomy.

Criterion B

Presence of minor criteria documented within 28 days of last exposure to IgPro10, consisting of:

- Direct antiglobulin test (DAT) positive
- Haptoglobin $<$ lower limit of normal
- Lactate dehydrogenase $>$ upper limit of normal
- Total or indirect (unconjugated) bilirubin $>$ upper limit of normal or jaundiced
- Hemoglobinuria or red / dark urine
- Hemoglobinemia
- Spherocytosis
- Hepatosplenomegaly

Subjects fulfilling criterion A and at least 2 of the minor criteria of criterion B, where 1 of the minor criteria must be DAT positive, will be considered to have hemolysis.

If an AE of hemolysis is reported it should be graded by the investigator using this scale:

- Grade 1 – Laboratory evidence of hemolysis only (eg, direct antiglobulin test, schistocytes, decreased haptoglobin)
- Grade 2 – Clinical evidence of hemolysis and ≥ 2 g/dL decrease in hemoglobin
- Grade 3 – Transfusion or medical intervention indicated (eg, steroids)
- Grade 4 – Life-threatening consequences; urgent intervention indicated
- Grade 5 – Death

Subjects with hemolysis Grade 3 and above will be assessed by an investigator or medically qualified designee whether it is in the best interest of the subject to continue the study and safe to continue the investigational treatment.

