10.3.3.3 Safety of IgPro10

Safety data of IgPro10 will be summarized in the same manner as IgPro20 as described in [Section 10.3.2.1](#). In addition, hemolysis will be analyzed descriptively.

10.4

CCI

CCI

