8.4 Values of Potential Clinical Importance

8.4.1 Laboratory Parameters

A laboratory value that is outside the reference range is either high abnormal (value above the upper limit of the normal (ULN) reference range) or low abnormal (value below the lower limit of the normal (LLN) reference range). An abnormal laboratory value is not necessarily of potential clinical interest.

Table 3: Potential Clinically Important Values: Laboratory Panels

Test Name or Test combinations (Test code in lab data transfer)	Outlier Criteria (in conventional units delivered by lab)
Chemistry Panel	
Bilirubin, total (TBILIARC)	>1.5 x ULN
Alkaline phosphatase (ALPARCH)	>2.5 x ULN
SGOT, AST (ASTARCH)	>3 x ULN
SGPT, ALT (ALTARCH)	>3 x ULN
Drug Induced Liver Injury (DILI) Screening	AST or ALT >3 x ULN and Total Bilirubin >2 x ULN*
Urea nitrogen (BUNARCH)	>2.5 x ULN*
Creatinine, serum (CREATARCH)	>1.5 x baseline assessment* or change >0.3mg/dL since last visit
Glucose, blood (non-fasting) (GLURNARCH)	<55mg/dL or >160mg/dL*
Calcium (CAARCH)	<7mg/dL or >11.5mg/dL
Total protein, plasma or serum (TPARCH)	<5g/dL* or >9g/dL*

Test Name or Test combinations (Test code in lab data transfer)	Outlier Criteria (in conventional units delivered by lab)
Albumin (ALBARCH)	<3g/dL
Sodium (NAARCH)	<130mmol/L or >150mmol/L*
Potassium, serum/plasma (KARCH)	<3mmol/L or >5.5mmol/L
Uric acid, serum (UAARCH)	>10mg/dL Males* , >8mg/dL Females*
Gamma Glutamyl Transpeptidase (GGTARCH)	>2.5 x ULN
Phosphorus, inorganic (PHOSARCH)	<2.5mg/dL or >5mg/dL*
Lactate dehydrogenase (LDHARCH)	>3 x ULN*
Hematology and Differential Panel	
Hemoglobin (HGB)	<10g/dL
Platelet count (PLT)	<75 x 10 ⁹ /L or >500 x 10 ⁹ /L*
White Blood Cell Count (WBC)	<3 x 10 ⁹ /L or >16 x 10 ⁹ /L*
Neutrophils, absolute (ABSNEUT) Neutrophils, differential (NEUT)	<1.5 x 10 ⁹ /L <40%*
Lymphocytes, absolute (ABSLYMPH) Lymphocytes, differential (LYMPH)	<0.8 x 10 ⁹ /L <10% or > 50%
Urine Panel	
Protein (UPROTNARCH)	>20mg/dL

*flag level based on CSLB medical monitor recommendation; all other levels are established as based on CTCAE v5.0 moderate grade.

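### No readable SAP section derives the protocol's composite hemolysis definition, so an IgPro10 subject who meets it can go uncounted if no AE coding to the SMQ is reported

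*SAP*

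**What the plan says.** Protocol 8.1.1.2 defines hemolysis in two parts. Criterion A is a "Drop in hemoglobin of > 1 g/dL within a 28-day interval since the time of last administration of IgPro10", with bleeding and repeated phlebotomy ruled out as explanations. Criterion B lists minor criteria: positive DAT, haptoglobin below the lower limit of normal (LLN), LDH or bilirubin above the upper limit (ULN), hemoglobinuria, hemoglobinemia, spherocytosis and hepatosplenomegaly. "Subjects fulfilling criterion A and at least 2 of the minor criteria of criterion B", with DAT positivity compulsory among them, count as having hemolysis. A grading scale follows, but it starts from a reported event: "If an AE of hemolysis is reported it should be graded by the investigator using this scale".

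Protocol 9.1.3 identifies the hemolysis AESI separately, by the broad hemolytic-disorders SMQ. Protocol 10.3.3.3 has IgPro10 safety summarized in the same way as IgPro20 and then says: "In addition, hemolysis will be analyzed descriptively".

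SAP 11.3 repeats the SMQ rule: the "classification of AEs into AESI categories will be done using standardized MedDRA queries (SMQ"). Sites also mark in the eCRF whether an AE is of special interest; of these marks it says "These entries are listed but not summarized". SAP 11.4 summarizes the Protocol 8.1.1 laboratory tests by scheduled visit. It adds changes from the reference visit and normal-range shifts for hematology and biochemistry, and a listing that flags out-of-range values.

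**The concern.** The protocol sets a study-specific test for who has hemolysis and schedules a panel 7 to 14 days after every IgPro10 dose to support it. The SAP carries forward only the AE-coding route. Between a panel that meets the definition and a count in the tables stand two steps: the investigator must report an AE (Protocol 8.1.1.9 makes this depend on a judgement of clinical significance), and its term must fall in the SMQ. If either fails, the subject's values appear in laboratory displays but the subject is not counted as a hemolysis case.

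Hemolysis is an important identified risk of IVIG in Protocol 1.4.1.2 and one of three AESIs. With 20 to 26 subjects, one case changes the reported percentage visibly. If the definition is first applied after database lock, its open details, above all which Hb is the comparator, would be chosen with the data in view.

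**Working it through.** The plan states no hemolysis rate or precision target, so there is no figure to reproduce. The check sets the protocol definition against the SAP outputs.

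| Element of Protocol 8.1.1.2 | Where the SAP shows it | What is absent |
|---|---|---|
| Hb fall > 1 g/dL within 28 days of IgPro10, no blood loss | 11.4: values, change from reference visit, shifts; Table 3: Hb < 10 g/dL | The > 1 g/dL fall, the 28-day window, the blood-loss exclusion |
| DAT positive (compulsory) | 9.3 at Screening; 11.4 as a Protocol Table 1 hematology test | Table 3 entry |
| Haptoglobin < LLN | 11.4 shifts | Table 3 entry |
| LDH > ULN | 11.4 shifts; Table 3 at > 3 x ULN | – |
| Bilirubin > ULN | 11.4 shifts; Table 3 at > 1.5 x ULN | – |
| A plus at least two of B, with DAT, in one subject | Nowhere | The whole combination |

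So most laboratory components are reported, and the composite is not. SAP 7.4 names the hemolysis assessment only to count assessments missed because of COVID-19. SAP 5 lists departures as small as a renamed analysis set but not this one.

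**Example subject (assumed values).** Hb goes from 14.0 to 12.4 g/dL, DAT is positive, haptoglobin is below LLN, LDH is 1.5 x ULN and bilirubin 1.2 x ULN.
- Criterion A: 14.0 − 12.4 = 1.6 > 1, met (no blood loss assumed).
- Criterion B: four minor criteria including DAT, met.
- Table 3: Hb < 10 no; LDH > 3 x ULN no; bilirubin > 1.5 x ULN no.
- SAP 11.4 shows each abnormal value separately. Without a reported AE that codes to the SMQ, no table counts the subject as hemolysis.

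**Panels available.** Four cycles per subject give up to 26 x 4 = 104 scheduled post-cycle panels, or 20 x 4 = 80 for 20 completers.

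**The Hb comparator.** IgPro10 is given at Weeks 1, 5, 9 and 13 (Sequence B) or 17, 21, 25 and 29 (Sequence A). Hemolysis panels fall at Screening and Weeks 3, 7, 11 and 15, or at Weeks 17, 19, 23, 27 and 31. No Hb is scheduled immediately before cycles 2 to 4, so the latest prior value is the panel after the previous cycle. The choice can decide a case. If the assumed fall from 14.0 to 12.4 passed through the midpoint 13.2 at the intervening panel, each step is 0.8 (Criterion A not met), while the total is 1.6 (above the threshold).

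**How often a case could be missed (illustration only; neither input is in the documents).** Let *p* be the proportion of subjects meeting the definition and *r* the probability that such a case is reported and codes to the SMQ. With independent subjects, P(at least one uncounted) = 1 − [1 − *p*(1 − *r*)]^N.
- *p* = 0.10, *r* = 0.80: *p*(1 − *r*) = 0.02, giving 1 − 0.98^20 = 0.33 and 1 − 0.98^26 = 0.41.
- *p* from 0.05 to 0.20 and *r* from 0.95 to 0.50: 0.05 to 0.88 for N = 20, and 0.06 to 0.94 for N = 26.

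The width of these ranges shows that the documents cannot settle the number.

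**The case against.** Four arguments on the other side carry weight.

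- A reader might infer that SAP 11.3 contradicts the protocol. It does not: Protocol 9.1.3 defines the hemolysis AESI by the same SMQ, and the endpoints in Protocol 2.1.2 and 2.2.2 count AEs and AESIs. For AESI counting there is no departure to declare.
- A reader might infer that up to 104 panels are never tested against the definition. The documents do not support this. Protocol 8.1.1.2 has clinical hemolysis assessed at the scheduled time points, and clinically significant laboratory findings must be recorded as AEs. What is missing is an independent derivation in the analysis.
- A reader might take the Table 3 cut-offs as the whole laboratory output. Table 3 is a general screen; the normal-range shifts in SAP 11.4 use the protocol's own limits for haptoglobin, LDH and bilirubin.
- A reader might argue that SMQ events without an Hb fall are false positives. Grade 1 on the protocol's scale needs laboratory evidence only and no Hb fall, and the SMQ's contents are outside the documents.

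It can also be said that the AESI tables in SAP 11.2 already are a descriptive analysis, and that Protocol 10.3.3.3 does not name Criteria A and B. This stands in part: the sentence is too brief to prove a breach. But it is worded as an addition to the IgPro10 safety summaries, in which Protocol 2.2.2 already places AESIs, and the SAP specifies nothing further for it.

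**Conclusion.** The gap is real but limited. No readable SAP section applies the composite definition, SAP 5 is silent on it, and a subject who meets it can go uncounted as hemolysis when no AE coding to the SMQ is reported. The documents support *can*, not *will*: sites assess hemolysis, and the component values stay in summaries and listings.

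Each missed subject is worth 3.8 percentage points of 26 or 5 of 20; the number missed cannot be estimated from the documents. The definition is tied to IgPro10 exposure, so the effect falls on the secondary IgPro10 safety objective. A reader might extend it to the primary IgPro20 endpoint, but the wording of Criteria A and B gives no basis for that. This should be fixed as a cheap improvement; the validity of the study does not depend on it.

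The conclusion rests on the readable text. The mock shells are separate documents, and SAP 8.2.9 to 8.2.21 and 10.1 are redacted, though the safety sections 11.2 to 11.4 are readable on this point.

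**What to change.** Keep the SMQ-based AESI tables and add a supportive analysis to SAP 11.3 and 11.4 for the IgPro10 periods:

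- Derive a subject-level and a cycle-level flag for hemolysis as defined in Protocol 8.1.1.2, including unscheduled samples.
- Pre-specify the Hb comparator, for example the most recent available Hb before the cycle, and state that for cycles 2 to 4 it may be the panel after the previous cycle.
- Review blood loss, phlebotomy and the clinical minor criteria (jaundice, dark urine, hepatosplenomegaly) at the DRM, before database lock.
- Report n (%) of subjects and of cycles, cross-tabulate against SMQ-based hemolysis AESIs and the site AESI flag, and list discordant cases.

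If the sponsor prefers not to do this, SAP 5 should declare the omission and give the reason.

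The cost is one derived variable, one table, one listing and some DRM time, with laboratory data already collected. The derivation will be approximate, because no Hb is scheduled immediately before cycles 2 to 4 and some criteria are clinical.
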